The proposed study will evaluate enhancements to our previous system tailored for the special needs of pediatric subjects: 1) A control strategy with responses to hyperglycemia and hypoglycemia spanning wide ranges, as is typical with children; 2) The use of time-dependent zones specific for pediatric subjects; 3) The development of models for young children, capturing the greater physiologic variability, and ensuring cautious insulin delivery; 4) remote alarming and notification systems that are useful to parents.

2. Objectives

The aim of this clinical study is to determine the feasibility, safety, and preliminary effectiveness of the Zone-Model Predictive Control Artificial Pancreas (ZMPC_AP) system in pediatric subjects with type 1 diabetes in an ambulatory semi-supervised environment over a short duration of 3 days and 2 nights, or up to 60 hours.

[figure not shown]

Figure 1. Outline of the proposed clinical study.

3. Study Overview

We will assess the feasibility, safety, and preliminary effectiveness of a Zone-Model Predictive Control Artificial Pancreas (ZMPC_AP) system in children and adolescents with type 1 diabetes. The study will simulate children's usual home environments, including meals of typical size and carbohydrate content, and will also include periods of afternoon exercise typical of after-school sports or other activities. This study will utilize a "hybrid" closed-loop paradigm, in which subjects (or parents) must count the carbohydrate content of the meals and announce this to the system at the time of the meal. Subjects and parents will be free to travel within a 15-minute walking distance of the study site, and they will sleep overnight in a local hotel, in which study personnel will provide on-site supervision. The duration of closed-loop control will be up to 60 hours. The initial cohort will be comprised of adolescent subjects, age 12-17y, and if successful (i.e. no stopping criteria are met), additional cohorts will consist of progressively younger-age children (8-12y and then <8y).

4. Study Subjects

a. Eligibility Criteria

Subjects will be eligible to participate in the study if they meet the following inclusion criteria:

- 1) Age <18 years; for first cohort(s), subjects will be 12-17 years; additional age brackets will be 8-11 years and then <8 years

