- 2) Type 1 diabetes for \geq 1 year duration – the diagnosis of type 1 diabetes will be based on the history of ketosis/ketoacidosis at diagnosis or laboratory evidence of islet-cell auto-immunity
- 3) A1c level \leq 10.0%
- 4) Use of insulin pump and carbohydrate counting for \geq 3 months
- 5) Current or past use of CGM is desirable but NOT required
- 6) Normal renal function as measured within 6 months of enrollment
- 7) Normal thyroid function within 6 months of enrollment, or if previously diagnosed with hypothyroidism, documented within 3 months of enrollment
- 8) Parent/guardian agrees to stay at hotel with subject for duration of hotel phase and has cell phone that can send/receive text messages
- 9) Subject and participating parent/guardian speak and comprehend English

b. Exclusion criteria

Subjects will be ineligible to participate in the study if they meet any of the following criteria:

- 1) Episode of diabetic ketoacidosis (DKA) within 6 months of enrollment
- 2) Episode of severe hypoglycemia (seizure, loss of consciousness) within 6 months of enrollment
- 3) Use of medications (other than insulin) known to affect BG levels within 4 weeks of enrollment – examples include systemic glucocorticoids, metformin, pramlintide, liraglutide, SGLT inhibitors)
- 4) Current use of other medications, that in opinion of investigator, would interfere with safety or effectiveness of the study including acetaminophen
- 5) Medical disorder, that in opinion of investigator, would be contraindication for inclusion; hypothyroidism and celiac disease are NOT exclusion if under good control
- 6) Female subjects of childbearing potential unwilling to have pregnancy testing
- 7) Female subject currently pregnant or lactating
- 8) History of alcohol or drug abuse, documented eating disorder, or inpatient psychiatric treatment within 6 months of enrollment
- 9) Subject is currently participating in another research study involving an investigational drug or device
- 10) Parent/guardian unable or unwilling to comply with study protocol and stay at hotel with subject for duration of study
- 11) Parent/guardian does not have cell phone with messaging capability

12) Parent/guardian does not comprehend written and spoken English

c. Source of Subjects

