A medical history will be elicited from subjects/parents, focusing on current diabetes management issues, prior diabetes-related history (date of diagnosis, complications and comorbidities), history of adverse events (severe hypoglycemia, DKA), other past and

current medical problems, medications, and allergies. For subjects already attending the Yale Children's Diabetes Program, electronic medical records will be available for each subject. For subjects not attending the Yale Children's Diabetes Program, copies of medical records will be requested. Demographic data including age, sex, race/ethnicity will also be recorded. Current pump settings, glucose meter and continuous glucose monitor (CGM) logs, will be reviewed and recorded.

2) Physical Examination

A focused physical examination will be conducted on all subjects, including vital signs, anthropometrics, cardiac, respiratory, abdominal, and neurological systems, thyroid, skin (particularly infusion sites), and pubertal staging.

3) Laboratory Data

Subjects' previous laboratory records will be reviewed, and a point-of-care A1c will be obtained at the visit, to confirm eligibility. Female subjects of childbearing potential will have a urine pregnancy test; those with a negative test will be invited to participate, and those with a positive test will be offered appropriate counseling.

4) CGM Placement

Subjects will be fitted with a DexCom sensor for collection of baseline glycemic profile data. Subjects already using a Dexcom CGM for their routine diabetes care may continue to use their own sensors; subjects not using Dexcom CGM will be provided with one and instructed on its proper use, including insertion, calibration, interpretation of data, recharging, and troubleshooting. Subjects/parents will be reminded that ALL insulin dosing decisions should continue to be made using capillary blood glucose testing with their usual meter, NOT the sensor. Subjects will be asked to collect baseline CGM data for up to two weeks.

5) Blood Glucose Meter

Subjects will be provided with a study glucose meter, which should be used for ALL BG testing during the baseline data collection period, as well as for calibration of the CGM. Subjects and parents will be instructed to test BG at least 4 times daily, more as needed, as per their usual home routine. Calibrations of the CGM should be done at least twice daily at appropriate times.

b. Hotel Visit

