Approximately 1-2 weeks after the enrollment visit, subjects and at least one parent/guardian will return for a "hotel" visit, of up to 60 hours, during which time the following will occur:

1) Initiation of Closed-Loop

Subjects will return to study site in the morning of the day of admission, for review of interim diabetes control and uploading of pump, meter and CGM data. Subjects' current

insulin pumps and sensors will be swapped for the study pump and sensor, and the system will be initialized and activated under study staff supervision. Study subjects will be trained on proper use of the system and will receive hard-copy training materials to use as reference. Before leaving the study facility, subjects will be required to demonstrate competency with basic system operations, and successful operation of the SMS alert system for subjects' and staff cell phones will be ensured. This training portion of the study may occur at the Yale Children's Diabetes Research Program facility or at a conference room at the study hotel.

2) Activities During Hotel Visit

Subjects will be encouraged to participate in usual daily activities, including exercise, eating out, shopping, etc) as long as they remain within a 15-minute walking radius of the study site, and they have a functioning cell phone with messaging capabilities. There will be age-appropriate scheduled activities with the study group as well as personal "down-time." During the entire duration of this phase, subjects will be under direct supervision of a parent or study staff member at all times. Subjects and parents will be required to return to hotel by 9 pm and have BG level checked at midnight each night they are at the hotel. A member of the study staff will be available at the hotel each night during the study to ensure subject safety and will check subjects' BG levels at midnight each night.

3) Exercise

Subjects will be encouraged to participate in exercise activities each day during the hotel visit, such as walking, jogging, exercise room, or sports. Exercise will not be announced to the controller, but subjects that usually pre-treat exercise with small amounts of carbohydrate may continue to do so after discussion with study staff. All subjects will check BG levels prior to and after the planned exercise.

4) Diabetes Management During Hotel Visit

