≥ 400	Any		Notify MD/NP SQ insulin correction, set change Suspend closed-loop May restart if the investigator concludes that the issue is related to a site failure and not due to malfunction of the controller, $BG 80-250\text{mg/dL}$ and ketones $< 0.6\text{ mmol/L}$. Encourage oral fluid intake.	Repeat BG and ketones in 1 hour
Any	>1.0 for $>2\text{h}$ or >3.0 once		STOP system Notify MD/NP SQ insulin correction, set change End closed-loop STOP study for this patient	Repeat BG and ketones in 1 hour

Any	Any	Abdominal pain, vomiting, altered level of consciousness	STOP system Notify MD/NP SQ insulin correction, set change End closed-loop STOP study for this patient Transfer to ER for further Tx	Per clinical scenario
-----	-----	--	---	-----------------------

9) End of Hotel Visit

At the conclusion of the hotel visit (afternoon of 3rd day), subjects will return to their usual pre-study insulin pump and regimen. Study devices will be returned and uploaded for data analysis. Subjects and parents will participate in semi-structured interviews and/or focus groups to give opinions about system usability, confidence in system safety, fear of hypoglycemia, and diabetes-related distress. Study staff will call subjects/parents approximately 24 hours after discharge to review BG control and assess for late adverse events.

10) Surveys and Interviews

Subjects and parents/caregivers will, at the conclusion of the hotel visit, complete several surveys/questionnaires to assess the effect of the closed-loop system on diabetes-related quality of life and distress, fear of hypoglycemia, and satisfaction with diabetes technology (see Table 2). Subjects and caregivers will also participate in focus groups or semi-structured interviews related to human factors issues, and perceived burdens and benefits, of the closed-loop system. Only the interviewer and participant(s) will be present during the interview/focus group.

Table 2. Surveys/questionnaires to assess effect of the closed-loop AP system.

CONSTRUCT:	MEASURE:
CHILD/ADOLESCENT SURVEYS	
Fear of hypoglycemia	Hypoglycemia Fear Survey
Diabetes burnout/burden	Problem Areas in Diabetes
Quality of life–diabetes specific	Pediatric QoL Inventory (PedsQL) – Diabetes Module (8-12)
Quality of life–diabetes specific	Pediatric QoL Inventory (PedsQL) – Diabetes Module (13-18)
Automated Insulin Delivery Device Acceptance	INSPIRE AID Acceptance (Draft) - Child

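### Minor: surveys meant to assess the effect of closed-loop are scheduled only once, after use, in a single-arm study, so no change or contrast can be formed

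*Combined protocol and SAP*

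**What the plan says.** Section 5.b.10 states the purpose and timing of the questionnaires together: "Subjects and parents/caregivers will, at the conclusion of the hotel visit, complete several surveys/questionnaires to assess the effect of the closed-loop system". The outcomes it names are diabetes-related quality of life and distress, fear of hypoglycemia, and satisfaction with diabetes technology. The title of Table 2 repeats the purpose: "Surveys/questionnaires to assess effect of the closed-loop AP system".

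Section 5.b.9 adds interviews or focus groups at the same time, in which families "give opinions about system usability, confidence in system safety, fear of hypoglycemia, and diabetes-related distress".

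The study has two visits (Section 5). Section 5.a lists five enrollment procedures: medical history, physical examination, laboratory data, CGM placement and the study glucose meter. For the hotel visit, Section 5.b.1 says "Subjects will return to study site in the morning of the day of admission", followed by data review and upload, the device change and training. Neither list contains a survey.

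The objective in Section 2 reads "The aim of this clinical study is to determine the feasibility, safety, and preliminary effectiveness" of the system and names no psychosocial outcome. Section 6 lists no survey score among the primary or secondary endpoints.

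**The concern.** Fear of hypoglycemia, distress, quality of life and satisfaction with glucose monitoring are states that a family already has on arrival. The background in Section 1 itself describes substantial parental anxiety, stress and fear of hypoglycemia before any use of this system. A single score taken after use combines that prior level with whatever change occurred, and nothing in the design separates the two.

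What is at stake is the reading of the survey results. The scores can be described, but they cannot show whether any of these states moved during the study, although both the section and the table title say that this is their purpose. A baseline not taken before closed-loop starts cannot be recovered later.

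**Working it through.** The plan gives no figure for the surveys, so there is nothing to reproduce. The check is whether any comparison can be built from the scheduled data.

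**Scheduled survey scores per person**

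| Time point | Source | Surveys listed |
|---|---|---|
| Enrollment visit | Section 5.a, items 1 to 5 | 0 |
| Admission, before closed-loop | Section 5.b.1 | 0 |
| End of hotel visit | Sections 5.b.9 and 5.b.10 | 1 administration |
| Control arm | none described | 0 |

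A within-person change is post minus pre. With no pre-use score it is undefined for every subject and parent. A contrast needs a second group, and there is none. Enrolling 24 or 48 subjects (Section 4.e) makes no difference.

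**Contrast with the glycemic data.** The plan does provide a baseline there: "Subjects will be asked to collect baseline CGM data for up to two weeks" (Section 5.a.4). Section 6.d then uses the pre-study glycemic profiles for comparison. The surveys carry the same kind of purpose without that step.

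**Where a baseline could go.** Let *w* be a form's recall period and *d* the time between its two completions. The two reports cover overlapping time when *w* > *d*. The documents give no recall periods.

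- Admission morning, before "insulin pumps and sensors will be swapped for the study pump and sensor" (Section 5.b.1): *d* is at most about 60 hours, the stated maximum length of the hotel visit.
- Enrollment: *d* is about 1 to 2 weeks plus up to 60 hours (Section 5.b).

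Enrollment therefore reduces overlap and memory of earlier answers. It also places the CGM run-in inside the interval. Section 4.a says "Current or past use of CGM is desirable but NOT required", so for subjects new to CGM the change would include starting it.

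**What a baseline would give (illustration only; it does not measure the defect).** The 95% half-width of the mean paired change, in SD units of the score, is t(0.975, n−1) × √(2(1−r)/n), where r is the within-person correlation. The documents do not give r, so 0.7 to 0.3 is assumed.

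- n = 24 complete pairs: 2.069 × √(0.6/24) = 0.33, to 2.069 × √(1.4/24) = 0.50
- n = 48: 0.22 to 0.34
- n = 8, the smallest cohort: 0.65 to 0.99

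The n = 24 and n = 48 lines assume a complete pair from every enrolled family. For child-reported forms this includes completion by children under 8, which Table 2 does not state. They do not apply to PedsQL, whose listed modules cover ages 8-12 and 13-18 and would have to be pooled.

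**The case against.** The strongest reply is that the plan never promises a within-person change. The surveys are ancillary, no endpoint or decision rule uses them, and opinions after use are a legitimate thing to collect. On that view only the wording is at fault.

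Much of this stands. The interviews and the INSPIRE device-acceptance forms make sense only after use and are not criticized. The reply does not reach the scales for fear, distress, quality of life and monitoring satisfaction, which the text ties to an effect that one post-use score cannot show.

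A second reply is that a baseline would not rescue the word *effect*. This is correct. A reader might infer that adding one would allow a device effect to be claimed. The documents do not support that: there is no comparator, and throughout the hotel stay subjects are supervised by a parent or staff (Section 5.b.2). Rewording is therefore needed in either case, and the value of a baseline depends on recall periods that the documents do not state.

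A third reply is that a survey time point may appear in Figure 1, the study outline, which is not shown in the text reviewed, or in the opening text, which was not available. This cannot be excluded. The detailed procedure lists give none; if the figure does, the text should be brought into line with it.

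**Conclusion.** The concern holds as a minor point. In the visible text the surveys are given once, after use, in a single-arm study, so their stated purpose cannot be met at any sample size. This conclusion needs no numerical assumption; it rests only on the written procedures being complete.

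Two stronger inferences should be resisted. One is that the trial's main conclusions are weakened: Sections 2 and 6 contain no psychosocial outcome, and continuation to younger cohorts does not depend on the scores. The other is that the absence of a listed PedsQL form for children under 8 adds to this point. That is a separate gap in coverage and says nothing about the missing baseline.

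**What to change.** 1. **Add a pre-use administration at an existing visit.** Give the Hypoglycemia Fear Survey, Problem Areas in Diabetes, PedsQL Diabetes Module and Glucose Monitoring Satisfaction Survey before closed-loop starts, in child and parent forms where listed.
   - State each form's recall period, and choose enrollment or the admission morning before the device change accordingly.
   - Report descriptively only any form whose recall period makes the two administrations overlap.
   - If enrollment is used, state that change includes starting CGM for subjects new to it.
   - Report paired change with 95% confidence intervals and the number of complete pairs. Keep child and parent reports separate and by-cohort results descriptive.
   - Leave the INSPIRE forms and interviews post-use only.

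2. **Reword Section 5.b.10 and the Table 2 title in either case.** With a baseline: *describe change after supervised closed-loop use*. Without one: *describe post-use scores*.

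No new visit or subjects are needed. The baseline costs a few extra forms per family. On the admission morning it may delay the start of closed-loop, and answers may be remembered over so short an interval. The rewording alone costs nothing.

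As a separate note, either list a quality-of-life form for the under-8 cohort or state that quality of life is not assessed there.

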If an individual subject has two episodes of a confirmed $BG < 50$ mg/dL (separated by at least 30 minutes), blood ketones > 1.0 mmol/L for over 2 hours, or any blood ketone level > 3.0 mmol/L, then the study will be stopped for that subject. Recall that subject will test for ketones after a confirmed $BG \geq 300$ mg/dL following CGM readings ≥ 300 mg/dL for > 1 hour. If any subject has a seizure, loss of consciousness or ketoacidosis ($CO_2 < 15$ mEq/L, or $pH < 7.3$) the study will be stopped for that subject and no additional subjects will be enrolled until the DSMB reviews the data.

If for any subject the $BG \geq 300$ mg/dL and blood ketones are > 1.0 mmol/L, the closed-loop control will be temporarily stopped, the infusion site will be changed, and supplemental insulin may be given at the discretion of the investigator. The closed-loop control will be restarted if $BG < 250$ mg/dL and blood ketones < 0.6 mmol/L.

If for any subject the $BG \geq 400$ mg/dL for any ketone levels, the closed-loop control will also be temporarily stopped, the infusion site will be changed, and supplemental insulin may be given if the investigator concludes that the issue is related to a site failure and not due to malfunction of the controller. The closed-loop control will be restarted if $BG < 250$ mg/dL and blood ketones < 0.6 mmol/L.

Additional information is shown in the Treatment Protocol table.

8) Treatment Protocol Table

Table 1. Hypoglycemia and hyperglycemia monitoring and treatment procedures.

Meter BG (mg/dL)	Ketones (mmol/L)	Clinical State	Action	Monitoring
Any		Seizure, loss of consciousness, or inability to consume oral treatment	STOP system Treat with SQ glucagon Notify MD/NP End closed-loop STOP study for this patient	Repeat BG every 15 minutes until $BG \geq 70\text{mg/dL}$
<70		Conscious, well-appearing	Treat with oral glucose Notify MD/NP Repeat MBG Continue closed-loop	Repeat BG every 15 minutes until $BG \geq 70\text{mg/dL}$
70-299		Asymptomatic and well	Continue closed-loop	Check BG (Premeal, pre and post exercise and midnight)
300-399	≤ 1.0	Asymptomatic and well	Continue with closed-loop Notify MD/NP May consider supplemental insulin	Repeat BG and ketones in 1 hour
300-399	> 1.0	Asymptomatic and well	Notify MD/NP SQ insulin correction, set change Suspend closed-loop May restart if $BG 80-250\text{ mg/dL}$ and ketones $< 0.6\text{ mmol/L}$. Encourage oral fluid intake.	Repeat BG and ketones in 1 hour

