Automated Insulin Delivery Device Acceptance	INSPIRE AID Acceptance (Draft) – Teen
PARENT OF YOUTH W T1D SURVEYS	
Fear of hypoglycemia	Hypoglycemia Fear Survey – Parent version
Diabetes burnout/burden	Problem Areas in Diabetes – Parent version
Quality of life–diabetes specific	Pediatric QoL Inventory (PedsQL) – Diabetes Module (8-12)– Parent version
Quality of life–diabetes specific	Pediatric QoL Inventory (PedsQL) – Diabetes Module (13-18) – Parent version

CONSTRUCT:	MEASURE:
Automated Insulin Delivery Device Acceptance	INSPIRE AID Acceptance (Draft) – Parent Version
ALL AGES	
Technology Acceptance	Comfort and Use of Technology Survey
Glucose Monitoring Satisfaction	The Glucose Monitoring Satisfaction Survey (GMSS)

6. Data Analysis

a. Primary Endpoint

The primary endpoint for the short-duration hotel study is safety, as defined as: 1) no more than one confirmed $BG < 50$ mg/dL; 2) no more than two confirmed $BG \geq 300$ mg/dL longer than 2 hours, unless determined to be from an infusion site failure; 3) no $BG \geq 400$ mg/dL; 4) no blood ketone level > 1.0 mmol/l for longer than 2 hours, or any ketone level > 3.0 mmol/L, unless determined to be from an infusion site failure; and 5) no significant adverse events, such as severe hypoglycemia (seizure, loss of consciousness), diabetic ketoacidosis.

b. Secondary Endpoints

Efficacy endpoints of interest will include:

- a. Mean meter and sensor glucose
- b. % Time in range (70-180 mg/dL)
- c. % Time below range (<70 mg/dL)
- d. % Time above range (>180 mg/dL)
- e. % Time in hypoglycemia (<60 mg/dL)
- f. % Time in hyperglycemia (>250 mg/dL)
- g. % time AP system active

The glycemic metrics will be calculated by total 24-hour period, and also broken down into daytime (6AM-11PM) and nighttime (11PM-6AM) periods.

c. Stopping

If an individual subject has two episodes of a confirmed $BG < 50$ mg/dL (separated by at least 30 minutes), blood ketones > 1.0 mmol/L for over 2 hours, or any blood ketone level > 3.0 mmol/L, then the study will be stopped for that subject. If any subject has a seizure, loss of consciousness or ketoacidosis ($CO_2 < 15$ mEq/L, or $pH < 7.3$) the study will be stopped for that subject and no additional subjects will be enrolled until the DSMB reviews the data.

d. Continuation

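### A subject stopped for high ketones can still be scored as meeting the primary safety endpoint, and item 1 can count one low glucose episode twice

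*Combined protocol and SAP*

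**What the plan says.** Section 6.a defines the primary endpoint as safety, in five items. Item 4 requires no blood ketone level above 1.0 mmol/L for longer than 2 hours, "or any ketone level > 3.0 mmol/L, unless determined to be from an infusion site failure". Item 2, which allows up to two confirmed glucose values of 300 mg/dL or more, has the same exception. Item 3, the limit at 400 mg/dL, has none: "longer than 2 hours, unless determined to be from an infusion site failure; 3) no".

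Sections 5.b.7 and 6.c set the individual stopping rule at the same two ketone limits, ending "or any blood ketone level > 3.0 mmol/L, then the study will be stopped for that subject". The Table 1 row for those limits gives "STOP system Notify MD/NP SQ insulin correction, set change End closed-loop STOP study for this patient". None of the three places makes an exception for site failure.

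Item 1 of 6.a allows at most one confirmed glucose below 50 mg/dL. The stopping rule acts on two such episodes at least 30 minutes apart. Section 5.b.5 and Table 1 have lows rechecked every 15 minutes until glucose is at least 70 mg/dL.

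Section 6.d bases progression to the next younger cohort on the stopping criteria and on DSMB review and approval, not on 6.a.

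**The concern.** Every item 4 event is also a stopping event, because the limits are identical. The endpoint can then set the event aside while the stopping rule cannot. What decides is whether the event is called an infusion site failure. Section 6.a does not say who decides, when, or on what evidence. Elsewhere the only named judge of site failure is the investigator, for management at glucose of 400 mg/dL or more, again without criteria.

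The other planned outputs may not reveal such a case. The secondary endpoints in 6.b contain no ketone measure. Section 8.a records hyperglycemic events as adverse events when they involve ketoacidosis; milder ketosis might enter as a device-related occurrence, but that is also an investigator judgement. Percent time with the system active would partly reflect an early stop, but not its reason.

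Item 1 errs in the other direction: counted by reading, it can fail a subject for one low that happened to be rechecked on schedule. With as few as 8 subjects per cohort, one classification in either direction visibly changes the primary safety count.

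**Working it through.** **Plan's own figure.** Section 4.e gives 8 to 16 subjects in each of three cohorts: 3 × 8 = 24 and 3 × 16 = 48, matching the stated 24–48. No alpha, power, target rate or event rate is given.

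**Step 1: apply both rules to the same subject.** Assume no glucose below 50, one glucose of 300 or more lasting over 2 hours, and no item 5 event.

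| Peak glucose (mg/dL) | Ketones (mmol/L) | Called site failure | Stopped | Meets 6.a |
|---|---|---|---|---|
| 350 | single value 3.2 | no | yes | no |
| 350 | single value 3.2 | yes | yes | yes |
| 350 | above 1.0 for 2.5 h, peak 1.5 | no | yes | no |
| 350 | above 1.0 for 2.5 h, peak 1.5 | yes | yes | yes, only if the exception covers the duration clause |
| 410 | either pattern | yes or no | yes | no (item 3) |

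The wording of item 4 leaves open whether the exception covers both ketone clauses or only the one above 3.0. The second row holds on either reading.

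**Step 2: size for item 4.** Let n be the number of subjects scored, with stopped subjects kept in the denominator, and k the number stopped for ketones whose event the exception can cover. The share meeting item 4 runs from (n − k)/n, if none is attributed to the site, to 100%, if all are. The values of k are assumptions.

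| n | k = 1 | k = 2 |
|---|---|---|
| 8 | 7/8 = 87.5% to 100% | 6/8 = 75.0% to 100% |
| 16 | 15/16 = 93.8% to 100% | 14/16 = 87.5% to 100% |
| 24 | 23/24 = 95.8% to 100% | 22/24 = 91.7% to 100% |
| 48 | 47/48 = 97.9% to 100% | 46/48 = 95.8% to 100% |

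For scale, the exact (Clopper-Pearson) 95% interval is 63.1–100% for 8/8 and 47.3–99.7% for 7/8.

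**Step 3: item 1 against 6.c.** Take meter readings 15 minutes apart.

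- 45, 48, 72: two readings are below 50, so by reading the count is 2, which exceeds 1 and fails item 1. The lows are 15 minutes apart, less than 30, so they are not two episodes under 6.c. The subject is not stopped.
- 42, 45, 49, 75: by reading the count is 3. Under 6.c it is 2 if spacing alone matters (0 and 30 minutes), or 1 if an unbroken low is one episode. The documents do not say which.

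**Step 4: site failure at glucose of 400 or more.** Section 5.b.7 ties the judgement to insulin: "supplemental insulin may be given if the investigator concludes that the issue is related to a site failure". Table 1 ties it to restarting: "May restart if the investigator concludes that the issue is related to a site failure and not due to malfunction of the controller". The two places give the judgement different roles and must be reconciled.

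**The case against.** An endpoint meant to judge the controller may reasonably set aside failures of the infusion site. That stands: the defect is not the exception but that it has no criteria and that no all-cause result is planned beside it.

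The Step 2 bounds concern item 4 alone. A subject excused there can still fail item 3 or item 5, so the change in the full endpoint can be smaller. That also stands. A reader might infer that every ketone-stopped subject can be scored safe; items 3 and 5 and the ambiguous scope of the exception rule that out.

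Because 6.a names no unit, a reader might infer that its limits apply to a whole cohort or study. That is implausible: item 1 mirrors a stop that applies to an individual subject at two episodes. The per-subject reading is the natural one and only needs stating.

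A reader might also infer that recovery after a set change can never indicate the cause, since Table 1 pairs it with an insulin correction. Section 5.b.7 does not support that for glucose of 300 or more with ketones above 1.0: "the infusion site will be changed, and supplemental insulin may be given at the discretion of the investigator". A set change without extra insulin is possible on that text.

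On item 1, the word confirmed is undefined. If the 15-minute recheck is itself the confirmation, 45 then 48 is one event and the mismatch disappears. The text does not say so, which is why the counting rule needs stating.

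**Conclusion.** The point holds in this form. A subject stopped for ketones above 3.0 mmol/L, with glucose below 400 and no ketoacidosis, can meet the primary safety endpoint on an unblinded attribution without stated criteria. One such subject in a cohort of 8 is worth 12.5 percentage points on item 4 (100 − 87.5). Item 1, if counted by reading, can fail a subject who had one low and was not stopped.

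The size rests on assumed counts, since the documents give no event rates. The consequence is limited. A reader might infer that the exception could let an unsafe cohort through to younger children; the documents do not support this, because progression under 6.d uses stopping criteria that have no exception, together with DSMB review. With no formal test or success threshold, what is at risk is the accuracy of the reported safety count, not a decision rule.

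**What to change.** These changes affect analysis only.

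1. In 6.a, report per subject the number and share meeting the endpoint with all events counted regardless of cause, beside the result with site-failure events excluded. List each subject who was stopped but met the endpoint, or was not stopped but failed it, with the recorded reason. With both results shown, the reader can see how much depends on the attribution.
2. Count item 1 by episodes separated by at least 30 minutes, as in 6.c, and state whether consecutive lows without recovery are one episode.

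The sponsor should also reconcile 5.b.7 and Table 1 on what the site-failure judgement governs at glucose of 400 mg/dL or more; no clinical rule is proposed here.

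The cost is a few lines in 6.a, one short listing and a recorded reason for each attribution. Visits, treatment and stopping do not change. The all-cause safety result may look slightly less favourable.
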